# PROTOCOL SYNOPSIS

Funder NIH-NIDDK  Clinical Phase N/A  Study Rationale More than eight million Americans each year experience unstable housing and/or homelessness; this includes 44% of all adults seen at community health centers. The chronically homeless have a 5- to 10-fold increased risk of premature death and high health care costs (driven by acute emergency department and hospital visits). Diabetes prevalence is approximately the same among the homeless versus general population (8%), but people with type 2 Diabetes who experience Homelessness, herein abbreviated as DH, have worse glycemic control and are hospitalized for diabetes complications a decade carlier and with more frequency than their housed peers. Managing diabetes while homeless presents a unique set of barriers including food insecurity, low social support, lack of safe medication storage/refrigeration. Almost half of people who are homeless have comorbid mental illness and/or substance use.  Prescription medications are a cornerstone in the management of type 2 diabetes and avoidance of complications. Diabetes medication adherence is low in housed populations, and limited evidence suggests it is as low or lower among DH; adherence is highly correlated with all-cause hospitalization and mortality.  We will consider the study feasible if we enroll 75% of those screened who meet inclusion criteria, and 75% of enrolled participants complete at least one follow-up. We will consider the intervention acceptable if 70% of participants are satisfied and would recommend it to others.  The goal of the current study is to conduct a randomized pilot trial of the D-HOMES program. D-HOMES is a coaching-based collaborative care intervention tailored to DH using behavioral activation, motivational interviewing and psychosocial support to improve medication adherence. We will compare this to brief diabetes education and referral to meet medical and psychosocial needs. Our team's central hypothesis is that medication adherence, glycemic control, health care use/cost will improv						
Clinical Phase  N/A  More than eight million Americans each year experience unstable housing and/or homelessness; this includes 44% of all adults seen at community health centers. The chronically homeless have a 5- to 10-fold increased risk of premature death and high health care costs (driven by acute emergency department and hospital visits). Diabetes prevalence is approximately the same among the homeless versus general population (8%), but people with type 2 Diabetes who experience Homelessness, herein abbreviated as DH, have worse glycemic control and are hospitalized for diabetes complications a decade earlier and with more frequency than their housed peers. Managing diabetes while homeless presents a unique set of barriers including food insecurity, low social support, lack of safe medication storage/refrigeration. Almost half of people who are homeless have comorbid mental illness and/or substance use.  Prescription medications are a cornerstone in the management of type 2 diabetes and avoidance of complications. Diabetes medication adherence is low in housed populations, and limited evidence suggests it is as low or lower among DH; adherence is highly correlated with all-cause hospitalization and mortality.  We will consider the study feasible if we enroll 75% of those screened who meet inclusion criteria, and 75% of enrolled participants complete at least one follow-up. We will consider the intervention acceptable if 70% of participants are satisfied and would recommend it to others.  The goal of the current study is to conduct a randomized pilot trial of the D-HOMES program. D-HOMES is a coaching-based collaborative care intervention tailored to DH using behavioral activation, motivational interviewing and psychosocial support to improve medication adherence. We will compare this to brief diabetes education and referral to meet medical and psychosocial needs. Our team's central hypothesis is that medication adherence, glycemic control, health care use/cost will improve with D-HOMES more than in our c	Study Title					
More than eight million Americans each year experience unstable housing and/or homelessness; this includes 44% of all adults seen at community health centers. The chronically homeless have a 5- to 10-fold increased risk of premature death and high health care costs (driven by acute emergency department and hospital visits). Diabetes prevalence is approximately the same among the homeless versus general population (8%), but people with type 2 Diabetes who experience Homelessness, herein abbreviated as DH, have worse glycemic control and are hospitalized for diabetes complications a decade earlier and with more frequency than their housed peers. Managing diabetes while homeless presents a unique set of barriers including food insecurity, low social support, lack of safe medication storage/refrigeration. Almost half of people who are homeless have comorbid mental illness and/or substance use.  Prescription medications are a cornerstone in the management of type 2 diabetes and avoidance of complications. Diabetes medication adherence is low in housed populations, and limited evidence suggests it is as low or lower among DH; adherence is highly correlated with all-cause hospitalization and mortality.  We will consider the study feasible if we enroll 75% of those screened who meet inclusion criteria, and 75% of enrolled participants complete at least one follow-up. We will consider the intervention acceptable if 70% of participants are satisfied and would recommend it to others.  The goal of the current study is to conduct a randomized pilot trial of the D-HOMES program. D-HOMES is a coaching-based collaborative care intervention tailored to DH using behavioral activation, motivational interviewing and psychosocial needs. Our team's central hypothesis is that medication adherence, glycemic control, health care use/cost will improve with D-HOMES more than in our comparison. This pilot trial is under-powered to assess efficacy and focuses on recruitment, retention, blinding, and randomization procedures.	Funder	NIH-NIDDK				
housing and/or homelessness; this includes 44% of all adults seen at community health centers. The chronically homeless have a 5- to 10-fold increased risk of premature death and high health care costs (driven by acute emergency department and hospital visits). Diabetes prevalence is approximately the same among the homeless versus general population (8%), but people with type 2 Diabetes who experience Homelessness, herein abbreviated as DH, have worse glycemic control and are hospitalized for diabetes complications a decade earlier and with more frequency than their housed peers. Managing diabetes while homeless presents a unique set of barriers including food insecurity, low social support, lack of safe medication storage/refrigeration. Almost half of people who are homeless have comorbid mental illness and/or substance use.  Prescription medications are a cornerstone in the management of type 2 diabetes and avoidance of complications. Diabetes medication adherence is low in housed populations, and limited evidence suggests it is as low or lower among DH; adherence is highly correlated with all-cause hospitalization and mortality.  We will consider the study feasible if we enroll 75% of those screened who meet inclusion criteria, and 75% of enrolled participants complete at least one follow-up. We will consider the intervention acceptable if 70% of participants are satisfied and would recommend it to others.  The goal of the current study is to conduct a randomized pilot trial of the D-HOMES program. D-HOMES is a coaching-based collaborative care intervention tailored to DH using behavioral activation, motivational interviewing and psychosocial needs. Our team's central hypothesis is that medication adherence, glycemic control, health care use/cost will improve with D-HOMES more than in our comparison. This pilot trial is under-powered to assess efficacy and focuses on recruitment, retention, blinding, and randomization procedures.	Clinical Phase	N/A				
type 2 diabetes and avoidance of complications. Diabetes medication adherence is low in housed populations, and limited evidence suggests it is as low or lower among DH; adherence is highly correlated with all-cause hospitalization and mortality.  We will consider the study feasible if we enroll 75% of those screened who meet inclusion criteria, and 75% of enrolled participants complete at least one follow-up. We will consider 50% session attendance as indicative of feasibility. We will consider the intervention acceptable if 70% of participants are satisfied and would recommend it to others.  The goal of the current study is to conduct a randomized pilot trial of the D-HOMES program. D-HOMES is a coaching-based collaborative care intervention tailored to DH using behavioral activation, motivational interviewing and psychosocial support to improve medication adherence. We will compare this to brief diabetes education and referral to meet medical and psychosocial needs. Our team's central hypothesis is that medication adherence, glycemic control, health care use/cost will improve with D-HOMES more than in our comparison. This pilot trial is under-powered to assess efficacy and focuses on recruitment, retention, blinding, and randomization procedures.	Study Rationale	housing and/or homelessness; this includes 44% of all adults seen at community health centers. The chronically homeless have a 5- to 10-fold increased risk of premature death and high health care costs (driven by acute emergency department and hospital visits). Diabetes prevalence is approximately the same among the homeless versus general population (8%), but people with type 2 Diabetes who experience Homelessness , herein abbreviated as DH , have worse glycemic control and are hospitalized for diabetes complications a decade earlier and with more frequency than their housed peers. Managing diabetes while homeless presents a unique set of barriers including food insecurity, low social support, lack of safe medication storage/refrigeration. Almost half of people who are				
screened who meet inclusion criteria, and 75% of enrolled participants complete at least one follow-up. We will consider 50% session attendance as indicative of feasibility. We will consider the intervention acceptable if 70% of participants are satisfied and would recommend it to others.  The goal of the current study is to conduct a randomized pilot trial of the D-HOMES program. D-HOMES is a coaching-based collaborative care intervention tailored to DH using behavioral activation, motivational interviewing and psychosocial support to improve medication adherence. We will compare this to brief diabetes education and referral to meet medical and psychosocial needs. Our team's central hypothesis is that medication adherence, glycemic control, health care use/cost will improve with D-HOMES more than in our comparison. This pilot trial is under-powered to assess efficacy and focuses on recruitment, retention, blinding, and randomization procedures.		type 2 diabetes and avoidance of complications. Diabetes medication adherence is low in housed populations, and limited evidence suggests it is as low or lower among DH; adherence is				
of the D-HOMES program. D-HOMES is a coaching-based collaborative care intervention tailored to DH using behavioral activation, motivational interviewing and psychosocial support to improve medication adherence. We will compare this to brief diabetes education and referral to meet medical and psychosocial needs. Our team's central hypothesis is that medication adherence, glycemic control, health care use/cost will improve with D-HOMES more than in our comparison. This pilot trial is under-powered to assess efficacy and focuses on recruitment, retention, blinding, and randomization procedures.		screened who meet inclusion criteria, and 75% of enrolled participants complete at least one follow-up. We will consider 50% session attendance as indicative of feasibility. We will consider the intervention acceptable if 70% of participants are satisfied and				
Study Objective(s) Primary		of the D-HOMES program. D-HOMES is a coaching-based collaborative care intervention tailored to DH using behavioral activation, motivational interviewing and psychosocial support to improve medication adherence. We will compare this to brief diabetes education and referral to meet medical and psychosocial needs. Our team's central hypothesis is that medication adherence, glycemic control, health care use/cost will improve with D-HOMES more than in our comparison. This pilot trial is under-powered to assess efficacy and focuses on recruitment, retention, blinding, and				
	Study Objective(s)	Primary				

	To conduct a randomized pilot trial of the D-Homes						
	intervention						
	Secondary						
	To refine efficacy measures for future D-Homes evaluation						
Test Article(s)	D-HOMES behavioral intervention to support medication adherence						
Study Design	Randomized pilot trial						
Subject Population Key Criteria for	We will enroll adults (age $\geq$ 18 yrs.) with type 2 diabetes who have experienced homelessness.						
Inclusion and Exclusion:	Inclusion criteria:						
	1. Age 18 yrs. or older						
	2. English-speaking						
	3. Recent homelessness by federal definition (HEARTH ACT)						
	a. Any housing instability in the last 12 mo. (includes supported housing or worry about paying rent)						
	
 
b. Significant housing instability in the last 24 mos. (includes any stay in shelter, outside, or places not meant for human habitation)
 
						
	4. Self-reported diagnosis of type 2 diabetes with A1c ≥7.5%, later verified in medical record and study point-of-care lab. test						
	5. Plan to stay in local area or be reachable by phone for the next 24 weeks						
	6. Willingness to work on medication adherence and diabetes self-care						
	Exclusion criteria:						
	1. Inability to provide informed consent (e.g., presence of a legal guardian, prisoners)						
	2. Active psychosis or intoxication precluding ability to give						
	informed consent						
N 1 040 11 1	3. Pregnant or lactating people.						
Number Of Subjects	Total Number of Subjects: 54						
	Total Number at Hennepin Healthcare: Unknown						
	Total Number of Sites: 1 (Hennepin Healthcare)						
Study Duration	Each subject's participation will last 24-30 weeks.						
	The entire study is expected to last up to 24 months.						
Study Phases	1. Screening : screening for eligibility and consent, baseline						
Screening	assessment						
Intervention	2. Randomization to:						
	
 
a. Intervention: study intervention with weekly coaching support in person and/or by phone x 12 week
 
						

	b. Comparison: one-time diabetes education session				
Follow-Up	3. Follow-up 1: 12-16-week follow-up assessments and A1c				
	Follow-up 2: 24-30-week follow-up assessments and A1c				
Efficacy Evaluations	• Satisfaction with trial, recruitment, retention rates				
	
 
Hemoglobin A1c measured by point-of-care fingerstick or venipuncture
 
				
	Self-reported medication adherence				
	Self-reported psychological wellness				
	Self-reported diabetes self-management, distress				
	
 
Height, weight, blood pressure
 
				
Safety Evaluations	Subject safety will be monitored by adverse events and rates of early termination of the study. We will also follow safety protocols in case we identify dangerous blood pressure values during assessment visits				
Statistical And Analytic Plan	We hypothesize a satisfactory, feasible, acceptable intervention with adequate recruitment and retention rates. We may see early indicators of improvement in efficacy measures of adherence, glycemic control, and wellness among intervention participants compared to comparison.				
	We will consider the study feasible if we screen 50% of those referred, enroll 75% of those screened who meet inclusion criteria, and 75% of participants complete follow-up. We will consider 70% session attendance as indicative of feasibility. We will consider the intervention				
	acceptable if 70% of participants are satisfied and would recommend it to others.				
	We will use generalized linear models to compare changes in A1c and medication adherence over time in intervention vs. comparison groups according to the ARMS-D measure of diabetes medication adherence while controlling for baseline differences and changes in housing status over time. Adherence will also be examined with pharmacy refill data (continuous medication gap for non-insulin diabetes medications 0-1.0). We will use an intention-to-treat approach including all randomized participants; multiple imputation will generate data for those lost to follow-up. Similar modeling approaches will compare psychological wellness, and other biometric and patient-reported outcomes.				
Data And Safety Monitoring Plan	[name] (PI) will work closely with study staff to monitor the quality of data collected at assessment. This pilot trial (N=54), does not meet NIH criteria requiring a Data Safety Monitoring Board				

(DSMB), however Drs. [name], [name], and [name] will oversee a detailed safety monitoring plan.

TABLE 1: SCHEDULE OF STUDY ASSESSMENT PROCEDURES

Study Phase	Eligibility screening	Consent, Baseline visit #1	Run-in, Baseline visit #2	Follow-up visit #1	Follow-up visit #2
Visit Number		1	2	3	4
Study Weeks, approximate	0	1	2-3	12-16	24-30
Confirm communication preferences	X	X		X	X
Review Inclusion/Exclusion Criteria	X	X	X		
Informed Consent		X			
Demographics/Medical History/Medication List		X	X		
Medical records and insurance access permissions		X			X
Biometrics: BP, Height, Weight, Hemoglobin A1c (fingerstick/venipuncture)		X	X	X	X
Medication review		X	X	X	X
Self-report survey measures:					
Mental Health Inventory (MHI-5) 			X	X	X
Health-related Quality of Life Short Form (SF-12) 			X	X	X
Problem Areas in Diabetes (5-item PAID) 			X	X	X
Diabetes self-management questionnaire (DSMQ) 			X	X	X
Adherence to Refills and Medications Scales-Diabetes (ARMS-D) 			X	X	X
Self-reported medication adherence (Adherence Starts with Knowledge, ASK-12) 			X	X	X
Basic needs survey 		X		X	X
Lifetime housing status		X			
Current housing status, 30 day recall		X		X	X
Use of substances (ASSIST)		X		X	
Self-reported health care use (NHANES)		X		X	X
Discrimination in Medical Settings Scale 117		X			
Client Satisfaction Questionnaire (CSQ-8) 95				X	

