# TABLE 2: SCHEDULE OF STUDY TREATMENT PROCEDURES

Intervention group,	Comparison group,
10 weekly coaching offered over 12 weeks	
Session #1 in-person on day of baseline assessment visit 2	1 educational session (15-30 min.) offered in-person on
Sessions #2-10 offered in-person or via phone/video	day of baseline assessment visit 2
Monthly booster calls from 12-24 weeks	Monthly calls to retain contact from weeks 3-30

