#### 2 BACKGROUND INFORMATION AND RATIONALE

### **OVERVIEW**

This protocol is for the third and final part of a set of studies with an overall goal to develop and pilot test the Diabetes Homeless Medication Support (D-Homes) program. D-Homes is a collaborative care intervention using motivational interviewing and behavioral activation alongside education and psychosocial support to improve medication adherence tailored to the experiences of people experiencing homelessness and diabetes (DH). Our team's central hypothesis is that medication adherence and diabetes self-care (and eventual glycemic control, health care use/cost) will improve with an intervention tailored to the unique context of DH.

This work builds upon part 1 (HSR#19-4622) during which we completed Aim 1 activities to develop the initial Diabetes Homeless Medication Support (D-Homes) treatment manual through focus groups with DH at various levels of glycemic control and interviews with their multi-disciplinary providers. Data from this phase has identified barriers and strategies for medication adherence, patient values regarding medication, and treatment preferences and informed development of part 2 (HSR #20-4863). Part 2 was a single arm treatment development trial that tested the feasibility and acceptability of study procedures and refined the D-Homes treatment manual through test cases (n=10-15). We found the D-Homes manual and study procedures are feasible and acceptable to DH as measured by self-report and post-treatment interview but that treatment engagement lessened for participants with the highest degrees of housing instability.

This protocol describes part 3, a fully randomized pilot study in concordance with study Aim 3.

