### 4.2 Allocation to Groups and Blinding

Participants will be randomized to either the intervention or a control group (1:1). Randomization will be stratified by housing type (unstable (e.g., shelter, staying outside) vs.

more stable (e.g., worry about rent payment, supportive or transitional housing)). Randomization will occur after baseline assessment visit #2 via REDCap. Staff who conduct who conduct the follow-up assessment visits will be blind to condition.

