# 4.3.2 Total Number of Study Sites/Total Number of Subjects Projected

Enrollment for the study will continue until 54 participants have been enrolled.

HHRI will serve as the only site for this study.

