### 5.2 Study Intervention

For participants randomized to the intervention group, they will be offered 10 coaching sessions over 12 weeks. These will be conducted in-person, via secure video, and/or by phone-based per participant preference and COVID-19 safety protocols. The treatment will center on providing diabetes education, motivational and goal-setting support, and resource and care coordination (Figure 2).

In-person assessment visits will be conducted at private spaces convenient to the participant including Hennepin Healthcare, Health Care for the Homeless sites, or at participant homes (see *Home Visit Protocol*).

All in-person assessment and treatment visits will follow current guidance from HHRI and Hennepin Healthcare about social distancing and use of personal protective equipment.

In-person treatment visits will be arranged that may include the participants home

Video visits will be conducted via a secure Zoom or Teams link (using HHRI, Hennepin Healthcare, and/or Hennepin County HIPAA secure technology) or Facetime if the participant is using an Apple device.

Phone visits will be conducted via a study or office phone or the PI's work phone. If participants have no working phone, a study phone will be issued to participants and will sign a Study Issued Cell Phone/Tablet Agreement (See *Phone/Tablet Agreement*).

Psychological approaches of behavioral activation and motivational interviewing will be used along with provision of educational materials and tools to support behavior change (See *Tools and Education Materials*). Coaches will tailor which tools and educational materials are given to which participants depending on participant need as well as the specific goals that are mutually set. E.g.) A participant with 10 medications per day may benefit from a pillbox with AM and PM slots. E.g.) A participant with many appointments for behavioral and physical health care may benefit from a pocket calendar. Financial value of tools ranges from \$4.99 (glucose log book) to \$17.91 (Adhesives for Continuous Glucose Monitor).

Approved communication channels will be used to support participant's goal setting (e.g. reminders) and arrange study related visits.

Participants will be offered up to 10 treatment visits over 12 weeks and monthly booster calls from weeks 12-24.

#### 5.2.1 Visit 1

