#### 7 STATISTICAL CONSIDERATIONS

# 7.1 Primary Endpoint

The primary endpoint of this study is the satisfaction of participants in this pilot randomized trial (via CSQ-8).

The feasibility and acceptability of study protocols for recruitment, retention, and randomization are also important. We will assess this by measuring our ability to recruit and retain participants, and the assessment and treatment visits we can deliver (i.e., participant's attendance and follow-up with scheduled sessions and treatment activities). In addition to above outcomes, we will carefully track the number and types of between-treatment communications with participants (who initiated communication; form of communication: text, calls, e-mails, etc.).

We will consider the study feasible if we enroll 75% of those screened who meet inclusion criteria, and 75% of enrolled participants complete at least one follow-up. We will consider 50% session attendance as indicative of feasibility. We will consider the intervention acceptable if 70% of participants are satisfied and would recommend it to others.

We will also analyze our primary clinical endpoint of change in A1c between intervention and comparison groups between baseline follow-up visit #1 (approx. 12-16 weeks)

if it changes from baseline to between intervention.

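### The session-attendance threshold for feasibility is 70% in one synopsis row but 50% in Section 7.1 and another synopsis row, and nothing says which governs

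*Combined protocol and SAP*

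**What the plan says.** Three places in the current text give an attendance criterion.

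- Protocol Synopsis, Statistical And Analytic Plan row: "We will consider 70% session attendance as indicative of feasibility".
- Section 7.1, Primary Endpoint: "We will consider 50% session attendance as indicative of feasibility".
- Protocol Synopsis, Study Rationale row: the same sentence as Section 7.1, also at 50%.

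Section 7.1 counts "participant's attendance and follow-up with scheduled sessions and treatment activities" among the things by which feasibility and acceptability are assessed. The sessions concerned are described in Table 2 ("10 weekly coaching offered over 12 weeks") and Section 5.2 ("they will be offered 10 coaching sessions over 12 weeks").

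The Statistical And Analytic Plan row departs from Section 7.1 in two smaller ways. Its 75% retention criterion refers to completing follow-up without naming a visit, where Section 7.1 asks for one follow-up or more. It also requires that half of those referred be screened, which Section 7.1 does not mention. The 75% enrolment criterion and the 70% satisfaction criterion are the same in both places.

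**The concern.** A feasibility threshold is useful only if it is fixed before the result is known. Here two incompatible values are in force for the same quantity, and the synopsis disagrees with itself as well as with the statistical section. A result between the two values could be labelled either way, and nothing in the plan prevents that choice from being made once attendance is known.

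This matters more in a pilot than it would in a confirmatory trial. The protocol says the study is not powered for efficacy, and Section 7.5 justifies the sample size only by the aims of feasibility and acceptability. Engagement is also an open question in this population: the Overview in Section 2 reports that in part 2 "treatment engagement lessened for participants with the highest degrees of housing instability". No attendance rate is given there, so nothing can be said about how likely a result in the disputed range is.

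**Working it through.** **Is the conflict real?** The attendance sentences differ only in the number. The 70% is not the satisfaction criterion misread, because each place states that criterion in its own sentence. Neither value comes from an amendment log. The 50% figure appears in two places (Section 7.1 and the Study Rationale row) and the 70% figure in one. The threshold is set by choice, and Section 7.5 gives no numerical inputs, so there is no calculation in the plan to reproduce.

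**Inputs for the size of the gap**

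- Total sample size 54, from Section 4.3.2: "Enrollment for the study will continue until 54 participants have been enrolled".
- Equal allocation, from Section 4.2: "Participants will be randomized to either the intervention or a control group (1:1".
- Ten sessions per intervention participant, from Table 2 and Section 5.2.
- Assumptions: all 54 are randomised, the split is exactly even, and every intervention participant has a denominator of 10.

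**Pooled reading (sessions attended ÷ sessions offered)**

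- Intervention arm: 54 / 2 = 27.
- Sessions offered: 27 × 10 = 270.
- 50% threshold: 0.50 × 270 = 135. 70% threshold: 0.70 × 270 = 189.
- Totals that meet 50% and miss 70%: 135 to 188.
- As percentages: 135 / 270 = 50.0% and 188 / 270 = 69.6%.
- As mean sessions per participant: 135 / 27 = 5.0 and 188 / 27 = 6.96.

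**Participant-level reading.** The plan does not define attendance. Suppose instead that the criterion is the share of participants who reach some required number of sessions (an assumption; the plan names no such number).

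- 0.50 × 27 = 13.5, so 14 participants are needed. 0.70 × 27 = 18.9, so 19 are needed.
- Results of 14 to 18 of 27 fall in the gap.
- Exact binomial chance of meeting each cut-off, for assumed true rates:

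| Assumed true rate | At least 14 of 27 (50%) | At least 19 of 27 (70%) |
|---|---|---|
| 50% | 0.500 | 0.026 |
| 60% | 0.855 | 0.184 |
| 70% | 0.986 | 0.577 |

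The rates are illustrative, since the documents give none.

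**Retention wording.** 0.75 × 54 = 40.5, so 41 people are needed (41 / 54 = 75.9%; 40 / 54 = 74.1%). The two wordings give different verdicts only if 41 or more attend at least one follow-up while 40 or fewer complete whatever the synopsis row requires. If that row also means one visit or more, there is no conflict. Section 3.1 lists follow-up to a final 24-week assessment among the pilot outcomes, so a stricter reading remains open.

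**The case against.** The strongest reply is that little depends on the number. Attendance is called only indicative and stands outside the sentence that defines when the study is feasible. The primary endpoint is CSQ-8 satisfaction, and no test, stop/go rule or sample-size calculation uses the threshold. The observed rate can be reported whatever the threshold. On this view the point is editorial, and after-the-fact selection is a possibility for which the documents offer no evidence. All of that is fair and limits the weight of the point, but it does not remove two incompatible values for one prespecified criterion.

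A second reply is that the session counts depend on one reading of attendance. This also stands. Section 5.2 elsewhere makes 10 a maximum, Section 4.3.1 allows four further weeks for missed visits, and the attendance sentence does not expressly exclude the comparison group's single education session. The counts of 135 to 188 are therefore illustrative. The percentage gap, from 50% to just under 70%, does not depend on these choices.

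A third reply is that the retention wording in the synopsis may just be shorthand for Section 7.1, and that the referral criterion is an addition and not a clash. Both are possible, so they remain secondary here. The referral criterion does, however, sit inside the sentence that defines feasibility, so whether it applies needs to be settled.

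**Conclusion.** The plan is wrong as written on this point and should be corrected. It sets two thresholds for session attendance, 50% and 70%, and gives no basis for choosing between them. Any attendance from 50% to just under 70% receives opposite labels. With 27 intervention participants and 10 sessions each, that is 135 to 188 of 270 pooled sessions. A smaller arm would shrink the counts but leave the percentage range unchanged. The documents do not show which value was intended, and no view is taken here. The effect is confined to one supporting indicator of feasibility and does not touch the primary endpoint or any treatment comparison. The differences in retention wording and the extra referral criterion are lesser points to settle at the same time.

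**What to change.** Before attendance and retention are tabulated, amend Section 7.1 to:

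1. State one attendance threshold.
2. Define attendance: pooled share of sessions offered, or share of participants reaching a stated number of sessions; which sessions count; and the denominator. Without this, a single percentage still leaves the verdict open.
3. State one retention definition that names the visit or visits required.
4. Say whether the criterion on screening half of those referred applies.

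Then make both synopsis rows identical to Section 7.1. If the data have already been tabulated, report attendance and retention against both versions and say that the plan was inconsistent.

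The cost is protocol wording only, with no new data or participants. The feasibility result may look less favourable under whichever version is adopted.
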